**I. Hypotheses and Specific Aims:**

We will conduct a two site randomized clinical trial (VA Eastern Colorado Health Care System [VA ECHCS] and VA Puget Sound [PSVAHCS]) to determine whether an intervention to improve symptoms and to help Veterans adjust to living with Chronic Heart Failure (CHF), Chronic Obstructive Pulmonary Disease (COPD) and Interstitial Lung Disease (ILD) improves quality of life. The intervention will also help Veterans communicate preferences for treatment with their providers. The intervention involves routine clinical care and no experimental drugs or devices. The results will be directly relevant to Veterans who suffer with these illnesses and their families, as well as to providers, leaders in VA Central Office, and other researchers. Furthermore, this study will generate information that supports the broader dissemination and implementation of the intervention and informs the development of future palliative care and team-based interventions in the VA. Specific aims include:

**Aim 1:** Determine the effect of the intervention on (a) quality of life as a primary outcome, and (b) depression, symptom burden, advance care planning communication and documentation, disease-specific health status, emergency department visits, hospitalizations, and mortality as secondary outcomes.

**Aim 2:** Examine the implementation of the intervention.

**Aim 2a:** Assess the degree, barriers, and facilitators of implementation of various intervention components. Identify which intervention components and processes are most critical from the perspectives of patients, intervention team members, and primary care providers whose patients received the intervention.

**Aim 2b.** Evaluate the resources (e.g., personnel time and other costs) associated with the intervention, and estimate the resources needed for implementation and maintenance of the intervention in other VA settings.

The brief study title is Advancing Symptom Alleviation with Palliative Treatment (ADAPT) and will be used with participants as it provides a simple acronym.

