**Figure 1. Conceptual Model & Proposed Intervention Effects**

**Palliative care need #2:** Few Veterans with CHF, ILD or COPD engage in advance care planning. Advance care planning is the process of considering and communicating healthcare values and goals. An advance directive is a legal document describing preferences for future care and appointing a surrogate to make health care decisions in the event of incapacity. While the benefits of completing an advance directive are controversial, recent studies demonstrate advance care planning can reduce health care costs; increase the likelihood of dying at home and receiving care aligned with one's wishes; decrease rates of hospital admission; and increase rates of hospice admission. Advance care planning also improves patient and family satisfaction and reduces stress, anxiety, and depression in surviving relatives. Despite these benefits and professional heart and lung organization recommendations, few Veterans with CHF, ILD or COPD engage in advance care planning. In addition, patients with CHF, ILD and COPD are often hospitalized at the end of life, although many say they would prefer to die at home.

**By addressing diverse symptoms and depression to improve quality of life, and implementing a successful advance care planning intervention, this study will overcome limitations of prior studies**

Despite disease-specific care in CHF, ILD, and COPD, patients experience poor quality of life. Disease management interventions in either illness have not consistently improved quality of life because they have not simultaneously addressed diverse symptoms and depression (Figure 1). In COPD, intensive pulmonary rehabilitation improves quality of life, but has limited reach as most veterans cannot access or receive pulmonary rehabilitation.

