12. Demographics/Study Form: Age, gender, race and ethnicity, education level, and clinical variables will be determined at the enrollment visit from the electronic medical record and patient self-report. For example, spirometry results (COPD), NYHA classification (CHF), etiology of CHF or COPD, most recent ejection fraction (CHF), and BNP or NT-pro BNP (CHF) will be documented. Medical history (including comorbidities), current medications, number of hospitalizations in the previous year will also be collected at the time of the enrollment visit. Patients' current care, including palliative care, mental health, cardiology, pulmonology, hospice and specialist pain care will be ascertained at baseline and 6 months. At the 6 and 12 month study visit, patients will be asked to relate interim events, including hospitalizations, the reasons for them, and for permission to obtain medical records relevant to such events from VA and non-VA facilities. Medications from the medical record will be documented again at the six month visit.

13. Advance care planning communication will be measured using patient report questions at the baseline and 6 month study visits. Advance directive documentation will be defined by the presence of any of the following notes in the electronic medical record at baseline and 6 months: advance directive discussion; scanned advance directive (either a living will or durable power of attorney for health care); or medical orders for life-sustaining treatment.

14. Hospitalizations/emergency room visits, mortality and risk of hospitalization and/or death: The following events will be assessed during the study period through VA and non-VA facility medical record review to supplement patient report: hospitalization (with cause) and mortality. We will also review medical records for intensive care use and end of life care patterns. We will also assess risk of hospitalization and/or death for participants during the study. Vital status will also be ascertained via the VA Vital Status File and the National Death Index.

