### Study population:

**Aim 1:** A total of 400 adult subjects will be randomized in a 1:1 ratio to one of 2 treatment arms: 1) enhanced usual care or 2) team-based palliative care intervention plus usual care. A component of the study intervention involves speaking to study subjects' informal (family) caregivers. The eligibility criteria (**Table 1**) aim to enroll Veterans with a diagnosis of CHF, ILD, or COPD who are at risk of hospitalizations or death, have poor quality of life, and are able to participate in the intervention.

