*Primary/Secondary Analyses.* Data from all participants will be included regardless of level of participation using an intent-to-treat approach. The primary outcome measure, FACT-G, will be analyzed as a continuous variable, while the secondary outcomes will be either continuous (disease-specific health status, depression, symptom burden, emergency department visits, hospitalizations) or binary (advance care planning communication and documentation; mortality). Due to the short follow-up period, time-to-event analyses will not be used. Analyses of the repeated measures, including primary and secondary endpoints, will be performed with SAS 9.4 using maximum likelihood estimation (MLE) for incomplete data using linear mixed models for continuous outcomes and generalized linear mixed models with a logit link for binary endpoints. This approach has several advantages: 1) all available data on eligible subjects can be included in the analysis even when there are missing data at follow-up, 2) MLE estimates the correlation between related measures and adjusts test statistics appropriately, 3) time-varying covariates can be incorporated into the model, if desired, and 4) the assumptions about missing data are relaxed from missing completely at random to missing at random. The primary analyses will not consider the pre-randomization variables, but the effect of these variables on outcomes will be investigated as secondary analyses. We will add a random intercept for PCP to the analytic models to account for clustering of outcomes by practice patterns.

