The primary outcome will be the difference in FACT-G score at 6 months. Because of the anticipated high correlation of baseline FACT-G with follow-up FACT-G ( $r>0.5$ ), we will include the baseline FACT-G as a precision variable in the mixed model. To describe the treatment by disease interaction, we will estimate the treatment effect and its confidence interval within each of the disease groups (CHF, ILD, COPD) using disease-specific health status measures (KCCQ, K-BILD, CCQ) at the 6 month endpoint. In exploratory analyses, we will estimate treatment effect within illness subgroups (CHF, ILD, and COPD) on the primary outcome, and within subgroups of illness, including CHF (preserved vs. reduced ejection fraction) and COPD (defined by spirometry and imaging). Missing data will be reviewed to identify potential patterns and examined to assess how these patterns impact our results. Specifically, we will examine plots of group means over time stratified by the time of the last completed observation to determine if biases are evident due to missing data. When data are missing at random, unbiased results can still be obtained from the likelihood method used in the analysis. To account for the possibility of data missing not at random, sensitivity analyses will be performed using pattern mixture models and results will be presented to assess the impact of missing data on the reported conclusions. Among those who were hospitalized or died, we will examine for differences in

intensive care utilization and patterns of care at the end of life. We will also examine for intervention effect on longer term health care utilization (e.g., hospitalization, intensive care utilization).

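### Intensive care use is to be compared among patients hospitalized or dead, a subset formed after randomization, and no all-randomized comparison is specified for the main study period

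*Protocol*

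**What the plan says.** Protocol section IV.F (Aim 1 Data Analysis) defines the comparison: "Among those who were hospitalized or died, we will examine for differences in" "intensive care utilization and patterns of care at the end of life". It gives no model, estimand, time window or descriptive label.

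The sentence after it reads "We will also examine for intervention effect on longer term health care utilization (e.g., hospitalization, intensive care utilization". It is not limited to the admitted or dead, but it states neither a population nor a period.

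Four other places bear on the point:

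- Section IV.F opens the primary and secondary analyses with a general rule: "Data from all participants will be included regardless of level of participation using an intent-to-treat approach".
- Section IV.A, item 14, covers data collection: "We will also review medical records for intensive care use and end of life care patterns". The review is not confined to admitted patients.
- Section I, Aim 1, lists "emergency department visits, hospitalizations, and mortality as secondary outcomes". Intensive care use is not in that list.
- Section II (palliative care need #2) says that advance care planning, which is part of the intervention, can "decrease rates of hospital admission; and increase rates of hospice admission".

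The SAP does not mention intensive care or end-of-life care.

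**The concern.** The two events that admit a patient to this comparison are outcomes of the trial, and the Protocol's own rationale expects the intervention may move at least one of them. Once the intervention influences who is in the subset, the arms being compared are no longer the randomized arms. Suppose it prevents mainly milder admissions. The intervention patients who are still admitted are then sicker on average, and a larger share of them will have used intensive care even if no additional patient did. If the intervention led to more mild admissions, the error would run the other way.

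At stake is a supplementary result that could be published with the wrong sign. A higher intensive care percentage in a palliative care arm would be easy to misread as harm.

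**Working it through.** The plan gives no rate, effect size or power for intensive care use, so there is no figure of its own to reproduce. The mechanism can be checked by arithmetic.

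**Inputs**

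- From the Protocol: "A total of 400 adult subjects will be randomized in a 1:1 ratio to one of 2 treatment arms", so 200 per arm. The sample size section anticipates 5% deaths, which is 0.05 × 200 = 10 per arm.
- Assumed: *h*, the proportion of an arm hospitalized or dead, and *p*, the proportion of the arm with any intensive care stay. Every intensive care patient is taken to be inside the subset, since such a stay is an admission.

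**Formulas**

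- Intensive care proportion in the subset: *g* = *p* / *h*.
- Subset risk ratio (intervention over control): *g*₁/*g*₀ = (*p*₁/*p*₀) × (*h*₀/*h*₁). The ratio per randomized patient is thus multiplied by *h*₀/*h*₁.
- Subset odds ratio: [*g*₁/(1 − *g*₁)] / [*g*₀/(1 − *g*₀)].

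**1. No effect per randomized patient; all averted admissions are non-intensive-care**

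| *h* control v intervention | *p*, both arms | Subset *g*, control v intervention | Odds ratio |
|---|---|---|---|
| 40% v 30% | 10% | 0.10/0.40 = 25.0% v 0.10/0.30 = 33.3% | 0.500/0.333 = 1.50 |
| 40% v 35% | 10% | 25.0% v 0.10/0.35 = 28.6% | 0.400/0.333 = 1.20 |
| 30% v 20% | 6% | 0.06/0.30 = 20.0% v 0.06/0.20 = 30.0% | 0.429/0.250 = 1.71 |

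In general, if *h* falls by 10%, 20% or 30% with *p* unchanged, the subset risk ratio is 1/0.9 = 1.11, 1/0.8 = 1.25 or 1/0.7 = 1.43, whatever the base rate.

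**2. No effect per randomized patient; mild admissions rise.** *h* goes from 40% to 48% and *p* stays at 10%. The subset shows 25.0% v 0.10/0.48 = 20.8%, ratio 0.83.

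**3. True benefit, sign reversed.** *h* goes from 40% to 32% and *p* from 10% to 9%. The subset shows 25.0% v 0.09/0.32 = 28.1%, although intensive care use fell by one percentage point.

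**4. Averted admissions carry average intensive care risk.** *h* goes from 40% to 32% and *p* from 10% to 8%. The subset shows 25.0% v 0.08/0.32 = 25.0%. The risk given admission is not distorted, but the fall from 10% to 8% per randomized patient cannot be seen.

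**Precision of the first example.** With 200 per arm it is 20/80 v 20/60. The standard error of the log odds ratio is √(1/20 + 1/60 + 1/20 + 1/40) = 0.376, so the 95% interval around 1.5 runs from about 0.72 to 3.14.

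**The case against.** **An unrestricted analysis is planned.** A reader might infer that intensive care use will be compared in this subset and nowhere else. The documents do not support that, because the next sentence plans an intervention-effect analysis of longer-term intensive care use without the restriction. What stands is narrower: that sentence gives no population or window, and it does not explicitly cover the main study period.

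**A change in admissions alone need not bias the result.** A reader might infer bias whenever the intervention changes the number admitted. Case 4 shows otherwise: if averted admissions are typical ones, the risk given admission is correctly equal. Distortion of that quantity needs a change in which patients are admitted or die. Even so, the subset then answers a different question and misses the reduction per randomized patient.

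**The weight is small.** Intensive care use is not a listed primary or secondary outcome, the SAP omits it, and no test is specified. A reader might suppose that the operational partners' decision on dissemination turns on it. Section II says instead that they gave most weight to staff time and costs, taken together with whether quality of life or advance care planning improves. This objection stands and sets the priority.

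**The sizes are assumed, and a single result would be imprecise.** Both are true. An interval of 0.72 to 3.14 would not justify a claim of harm, but imprecision does not remove a bias in the estimate.

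**A shift would be visible.** Hospitalizations and deaths are compared by arm anyway, so a careful reader could detect a change in subset size. That helps detection but does not correct the comparison.

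**End-of-life care can be described only in people who died.** This is largely so. It argues for a descriptive label, not for dropping the results.

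**Conclusion.** The concern holds in a limited form. The comparison among hospitalized or dead patients is not protected by randomization if the intervention changes which patients enter that subset, and the Protocol's rationale makes such a change plausible. Under the assumed rates, a null effect per randomized patient appears as an odds ratio of 1.2 to 1.7 when only non-intensive-care admissions are averted, and as a risk ratio of 0.83 when mild admissions rise. A small true benefit can appear as harm. With averted admissions of average risk there is no spurious difference, but a real reduction is hidden. None of these rates comes from the documents. They show the direction and possible size of the error and do not forecast it.

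The trial's main conclusions do not rest on this analysis, so the priority is low. The change is still worth making because the stated denominator can mislead and a better one is available from records already being reviewed.

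**What to change.** Replace the sentence in section IV.F, and add the same text to the SAP, so that it says:

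- Intensive care use (any stay, and days) is compared between arms in all randomized patients over a stated study window, with zero for those never admitted.
- Results among hospitalized patients, and end-of-life care patterns among those who died, are descriptive. They are shown beside the numbers hospitalized and dead in each arm. At the anticipated 5% mortality, the decedent table would rest on about 10 patients per arm.
- The longer-term utilization analysis has a named population and time window.

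The cost is a few lines of wording and no new data collection. The downside is a lower event proportion, for example 10% of all randomized patients instead of 25% of those in the subset. With 10% in each arm of 200, the 95% interval for the difference is about ±1.96 × √(2 × 0.10 × 0.90 / 200) = ±5.9 percentage points, so modest effects will remain uncertain. Patients who die early have less time to accrue intensive care days, which is a further reason to print deaths per arm alongside.

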### **Aim 2a Data Analysis**

The quantitative data on intervention component implementation will be examined using descriptive statistics. For example, for team meetings, the number and type of medical orders written and completed will be summarized. For social worker visits, the median, range, interquartile range, and types of modules completed will be displayed. This type of analysis was completed for the pilot study and will show what components of the intervention were actually done. It will characterize the true “dose” and content of the intervention that was provided. This will contribute information about what may have led to intervention success or failure.

The data on intervention components and processes will be analyzed using a combination of inductive and deductive methods. We will create an evolving set of codes linked to units of text (fragments, sentences or paragraphs) using the Atlas.ti software package. A qualitative analyst and the research assistant will serve as primary coders for qualitative data, and PI will review coding and codebooks as they are developed. We will follow a systematic process to enhance coder agreement in assigning codes and a peer debriefing process that requires regular meetings with a qualitative analyst, the PI, and the research assistant to review and refine codes, code definitions and conceptual boundaries for our analysis. The iterative analysis will begin by using the a-priori codes based on the CFIR model (Table 6), supplemented by codes reflecting intervention content and structure and questions used for data collection. Codes will be refined and new codes added as new insights emerge. Through systematic coding we will quickly develop working themes and hypotheses about critical intervention components and processes that will be examined (and inform any minor changes in data collection interview guides/survey). These themes will also describe facilitators and barriers to intervention implementation. We will both audio-record and take detailed notes during all data analysis meetings in order to document proposed codes and code revisions, proposed themes and their descriptions, and other decisions made during these working meetings.

We will use several recommended strategies to enhance the validity or credibility of qualitative findings: (1) structured interview guides administered by well-trained interviewers, (2) coding templates and detailed descriptions of codes, coding decisions and analysis strategies to document all phases of the data analysis (audit trail); and (3) team approaches (at least two analysts) to develop coding templates and independently code subsets of transcripts/notes to determine their agreement and application of codes and code definitions.

In addition to analyzing and summarizing quantitative (implementation tracking database and provider surveys) and qualitative (patient interviews and intervention team focus groups) findings separately, we will also merge findings to draw overarching lessons learned from multiple methods used. In this process, findings will be summarized in a table placing qualitative themes side by side with the quantitative findings to show the extent to which the data converges. Merging these findings will provide “triangulation”: findings from each data source will be used to validate and confirm findings from the other data sources. With the combination of qualitative and quantitative data, we expect to provide a more complete explanation of why certain intervention components and processes are more critical than others, as well as facilitators and barriers to the implementation of the intervention.

### **Aim 2b Data Analysis**

We will first calculate the resources (personnel hours or FTE, and other costs) to implement and maintain the intervention during the study. Personnel costs associated with the program will be calculated based on actual VA nurse (and other staff) wage and benefit rates. Total intervention costs and costs per intervention participant at each site will be calculated. Actual salaries and benefits will be used when calculating personnel costs. Second, we will estimate the resources and costs to implement and maintain the program in a variety of VA settings.

Several sensitivity analyses will estimate the range of intervention costs using alternative assumptions for costs that may vary in different implementation contexts. Three sensitivity analyses are planned: (1) variable labor costs with more or less experienced nurses or physicians; (2) variable efficiency of the nurse and social

worker in part-time vs. full-time intervention roles; this will be done using actual data that reflect the range of time spent per patient early in the study vs. later in the study; (3) variable patient case mix using the range of time spent per patient. In exploratory analyses, we will estimate which patient-level predictors (e.g., cardiac ejection fraction, spirometry, quality of life) are associated with time spent per patient (outcome) using linear regression models.

## **G. Summarize Knowledge to be Gained**

The proposed study is significant because it aims to improve quality of life and provision of care according to Veterans' goals and preferences in common, burdensome illnesses. The study is innovative because it (1) tests the effectiveness of palliative care in CHF, ILD, and COPD, leading causes of death among Veterans; (2) combines palliative and disease-specific care for symptoms with psychosocial treatment for depression to improve quality of life; and (3) leverages the skills of affiliate health providers (nurses, social workers) to provide basic palliative care, with physician supervision; and (4) uses an hybrid effectiveness/implementation design to increase the relevance to operations leaders and future research. The research team has expertise in behavioral and health care delivery clinical trials, CHF, ILD and COPD, and implementation science.

